 - c. Not nearly enough to be helpful
 - d. Don't know/prefer not to answer

[PediCARE Recipients only]

5. How likely would you be to recommend participation in the PediCARE support program for other families undergoing childhood cancer treatment?
 - a. Very likely
 - b. Somewhat likely
 - c. Somewhat unlikely
 - d. Very unlikely
 - e. Don't know/prefer not to answer

6. Did the PediCARE support program make it easier to meet any of the below basic needs (choose all that apply)?
 - a. No
 - b. Yes, easier to buy food for my family
 - c. Yes, easier to get to and from hospital/clinic

7. How much of the food money provided would you say you used each month?
 - a. All
 - b. Most
 - c. Some
 - d. Very little
 - e. None

8. If you did not use most/all of the food money, what were the main reasons?
 - a. Not applicable
 - b. Didn't need it
 - c. Forgot about it
 - d. Hard to use
 - e. Saving money for if finances get harder
 - f. I don't know
 - g. Other (please specify): _____

9. If you used any of the food money provided, how easy or difficult was it to buy groceries for your family with this approach?
 - a. Not applicable
 - b. Very easy
 - c. Somewhat easy
 - d. Somewhat difficult
 - e. Very difficult

10. About how many of the 8 roundtrip Ride Health rides provided each month would you say you used?

- a. Not applicable
- b. None
- c. 1 - 2
- d. 3 - 4
- e. 4 - 5
- f. 5 - 6
- g. 6 - 7
- h. 7 - 8

11. If you did not use all of the Ride Health rides, what were the main reasons?

- a. Not applicable
- b. Didn't need it
- c. Forgot about it
- d. Hard to use
- e. Didn't like this type of transportation
- f. I don't know
- g. Other (please specify): _____

12. How much of the gas card money provided would you say you used each month?

- a. Not applicable
- b. All
- c. Most
- d. Some
- e. Very little
- f. None

13. If you did not use most/all of the gas cards, what were the main reasons?

- a. Not applicable
- b. Didn't need it
- c. Forgot about it
- d. Hard to use
- e. Saving money for if finances get harder
- f. I don't know
- g. Other (please specify): _____

14. Would you say the PediCARE program helped you address other basic needs at home (such as heat or electricity bills, rent or mortgage)?

- a. Definitely
- b. Somewhat
- c. Not at all

15. If the PediCARE program were to be redesigned and what types of other supports would be more helpful? _____

We have come to the end of the questionnaire.

To be completed by administering research staff.

Today's date (month/day/year): ___ / ___ / _____

Site at which survey administered:

- a. DFCI
- b. UAB

Name of staff member administering survey (Last, First): _____

Survey administered:

- a. English, US
- b. Spanish, US

Interpreter used:

- a. Yes (specify language): _____
- b. No

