8.0 Study Endpoints

8.1 Feasibility: The primary endpoint of this study is feasibility. Feasibility will be defined as at least 75% consent to randomization and at most 20% attrition per arm. We will assess process barriers to feasibility including recruitment, attrition by arm and parent report of PediCARE component utilization (i.e. food and transportation).

[figure not shown]
Study Timeline (Months)	Months 1 -6 Year 1	Months 7- 12 Year 1	Months 1-6 Year 2
Screen and enroll families (6 months)			
Intervention administration (6 months)			
Data analysis			

8.2 HMM and Utilization: The secondary endpoints of this study will be used to generate effect size estimates to support planning of a subsequent RCT. Secondary endpoints will be evaluated comparing recipients of PediCARE versus Usual Care. Secondary outcomes include change in HMM utilizing an HMM score (range 0-4) at 6-months compared to baseline; and proportion of patients experiencing an Emergency Department (ED) visit or Intensive Care Unit (ICU) admission over 6-months.

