- At study entry, the site CRA will assist families randomized to PediCARE in creation of an Instacart account for online grocery purchasing and delivery. Account creation requires

a name, email address, telephone number, home address for grocery delivery, and a credit card, debit card, or gift card

- Families will subsequently be provided a monthly pre-paid allocation of Instacart funds the beginning of each month of study participation. Families will choose and order groceries at their discretion over the course of the study.
- Other logistics: Instacart grocery ordering can be performed on any smartphone or computer with internet access. Any enrolled family without access to either a smartphone or computer will be provided with access to an iPad in clinic or while inpatient for ordering. Groceries can be ordered for same-day or future delivery. Families who live in ZIP codes where Instacart delivery is not available (approximately 15% of the U.S.) will be provided with an equivalent dollar amount grocery gift card to their local grocery store.

(2) Transportation: Families will be provided with the option of either 48 round-trip rides (96 legs) over the course of six months to use as needed each month using RideHealth or (b) gas cards and parking passes to support an estimated 8 clinic/hospital visits per month. The flexibility of choosing which direct transportation support will best facilitate a family's ability to bring their child to clinic or the hospital is based on qualitative parent feedback from the PediCARE pretest.

(a) Transportation will be provided via RideHealth, a company which provides a HIPAA-compliant digital platform to coordinate patient transportation utilizing Uber/Lyft and other commercial ride services, a web-based on-demand transportation platform. This platform allows for HIPAA-compliant account generation using PHI on the back-end, and then links to ride-scheduling with Uber/Lyft or other commercial drivers on the front-end without PHI. Built for healthcare, RideHealth allows ride-authorization for patients between specified sites (i.e. home and hospital/clinic). Rides are booked by the parent, and can be booked in advance (e.g. for a planned clinic visit or hospital stay) or on-demand 24-hours a day via their website or dedicated call center (e.g. for unplanned clinic or Emergency Department visits). RideHealth provides real-time analytics on utilization and performance including timeliness and cost.

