- At study entry, the lead-site CRA will create a RideHealth account for families randomized to PediCARE within the central DFCI RideHealth account. Families can view only their own information to facilitate ride requests. Each account will include pre-authorization for 48 round-trip rides (96 legs) over six months.
- The local site CRA will educate families on utilization of the RideHealth patient-facing app to request rides (process is similar to Uber/Lyft app for ride scheduling)
- Ride data including utilization, cost, and time will be provided to the lead site linked to study ID by RideHealth

(b) Families will be provided with gas cards in a dollar amount stratified by distance from hospital based on estimated average frequency of clinic visits/hospitalization and 2018 gas costs. Specifically, families who live <180 miles from the hospital will be provided with \$200/month in gas cards; those who live \geq 180 miles from the hospital will be provided with \$300/month in gas cards. Families will receive 8 parking passes per month at sites where families pay for parking.

PediCARE will provide both groceries and transportation support to all intervention recipients for the duration of the study. Pilot families will be randomized 1:1 at each site to receive the

PediCARE intervention or UC for 6-months which represents the most intensive phase of treatment for children with leukemia and neuroblastoma and covers the duration of chemotherapy treatment for most solid tumor and lymphoma diagnoses.

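### Ride use, a descriptive process measure, is assigned to a parent-report item with overlapping answers, while the RideHealth ride log has no stated role in that measure

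*Combined protocol and SAP*

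**What the plan says.** Section 8.1 sets the primary endpoint: "Feasibility will be defined as at least 75% consent to randomization and at most 20% attrition per arm". It then says that process barriers will be assessed, and lists among them "parent report of PediCARE component utilization (i.e. food and transportation").

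For rides, the parent report comes from item 10 of the follow-up survey's Assessment section, asked of PediCARE recipients only: "About how many of the 8 roundtrip Ride Health rides provided each month would you say you used". The options are Not applicable, None, 1-2, 3-4, 4-5, 5-6, 6-7 and 7-8.

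Section 9.3.2 describes the allotment as "48 round-trip rides (96 legs) over the course of six months to use as needed each month" and says of the account set-up: "Each account will include pre-authorization for 48 round-trip rides (96 legs) over six months". Families may instead choose "gas cards and parking passes to support an estimated 8 clinic/hospital visits per month". For those who take rides, the same section states: "Ride data including utilization, cost, and time will be provided to the lead site linked to study ID by RideHealth".

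Section 11 plans to describe, for the PediCARE arm, cost per patient and the share of families who received every component. It names no data source for that share and does not mention the ride log.

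**The concern.** Three features of the plan sit badly together.

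- **Overlapping answers.** Two families with the same ride use can be recorded in different categories. Nothing in the survey data would allow the categories to be separated afterwards.
- **A monthly frame for a pooled allotment.** The item treats the rides as a fixed 8 per month. Section 9.3.2 lets families draw on the pool as needed.
- **The weaker source is the one named.** Section 8.1 points to parent report. That means recall over six months, preferably read aloud by study staff (section 9.1.3), and it exists only for families who complete the follow-up survey. A count by study ID will be at the lead site and does not depend on survey completion, yet no section says it will be used for this purpose.

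What is at stake is the quality of a planning figure. The pilot is meant to prepare a multi-center trial, and ride uptake is a natural input to its budget and delivery plan.

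**Working it through.** **1. Does item 10 enter the feasibility decision?** Section 11 bases the decision on exact 90% confidence intervals for consent and 6-month completion. The exact (Clopper-Pearson) limits for x of n are: lower = Beta quantile at 0.05 with parameters (x, n−x+1); upper = Beta quantile at 0.95 with parameters (x+1, n−x).

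| Quantity | x/n | Estimate | Exact 90% CI | Target within the upper bound? |
|---|---|---|---|---|
| Consent | 39/60 | 65.0% | 53.6-75.2% | yes (75%) |
| Consent, one fewer | 38/60 | 63.3% | 51.9-73.7% | no |
| Completion | 28/40 | 70.0% | 56.0-81.7% | yes (80%) |
| Completion, one fewer | 27/40 | 67.5% | 53.4-79.6% | no |

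The plan's two thresholds, 39 and 28, reproduce. Neither uses ride data, so no answer to item 10 can change the decision.

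**2. How many ride counts are ambiguous?** Setting each monthly count against the printed options gives:

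| Rides in a month | Matching options |
|---|---|
| 0 | None |
| 1, 2 | 1-2 |
| 3 | 3-4 |
| 4 | 3-4 or 4-5 |
| 5 | 4-5 or 5-6 |
| 6 | 5-6 or 6-7 |
| 7 | 6-7 or 7-8 |
| 8 | 7-8 |
| 9 or more | no option |

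Four of the nine counts from 0 to 8 fit two boxes, and four of the eight non-zero counts (4/8 = 50%). As an example, a family using 4 of 8 rides (50%) can be placed in 3-4, which spans 3/8 to 4/8 (37.5% to 50%), or in 4-5, which spans 4/8 to 5/8 (50% to 62.5%).

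**3. Monthly figure against pool.** 48 round trips × 2 = 96 legs, and 48/6 = 8 per month, so the totals agree on average. They differ in form. For illustration only, a family taking 12 rides in each of two months and 6 in each of four uses exactly the pool (2 × 12 + 4 × 6 = 48), but item 10 has no answer for its two busy months.

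**4. Who contributes data.** The PediCARE arm has 14 + 6 = 20 families (section 4.0). Attrition of 20%, the most that section 8.1 allows per arm, is 0.20 × 20 = 4 families with no parent report. The rule in section 11 accepts 28 of 40 complete across both arms, which leaves 40 − 28 = 12 incomplete, without fixing how they divide between arms. The ride log would still hold the rides of such families if they chose rides.

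**5. What cannot be computed.** The documents give no distribution of ride use and no split between rides and gas cards. The number of families misclassified is therefore unknown.

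**The case against.** The best reply is that little is lost. If an exact count reaches the lead site, one ambiguous survey line removes no information, and the team can report the count. The list in section 8.1 is not presented as exhaustive, section 11 leaves the source for receipt of components open, and sections 6.1 and Appendix D provide for monitoring of intervention fidelity. Parent report also has work to do. No log is described for gas cards or parking passes, section 10.3 says the team has no access to families' Instacart accounts, and item 10 leads into item 11, where families give reasons for not using rides.

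Most of this stands, and it rules out three stronger readings that a reader might infer:

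- *That item 10 undermines the primary endpoint.* Sections 8.1 and 11 define and decide feasibility on consent and on attrition or completion. Utilization has no threshold.
- *That the ride log will be ignored.* The documents do not say so. They only leave its analytic role unstated.
- *That parent report is needless.* For gas cards and for reasons for non-use it is the only source described.

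The reply does not repair the item. Section 8.1 still names parent report for transportation, and anyone following it literally would tabulate ambiguous answers from survey completers only.

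**Conclusion.** The point holds as a minor one. Item 10 has overlapping options at 4, 5, 6 and 7 rides, has no option above 8, and does not match the pooled allotment in section 9.3.2. Section 8.1 names this parent report as the source for transportation use, and neither it nor section 11 gives the RideHealth data a role in that measure. The effect is confined to a descriptive process measure in an arm of 20 families, and within it to those who choose rides. The feasibility decision is unaffected. The count of ambiguous values assumes that families answer in whole rides per month. The advantage of the log assumes that RideHealth supplies the data as section 9.3.2 describes.

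**What to change.** 1. In sections 8.1 and 11, state that ride use among families who choose rides will be reported as RideHealth-logged round trips out of 48 per family (equivalently legs out of 96), including families without a 6-month survey.
2. Keep parent report for food, gas cards and reasons for non-use.
3. Make the item 10 options mutually exclusive: Not applicable, none, 1-2, 3-4, 5-6, 7-8, more than 8. Not applicable must stay, so that families who chose gas cards are not recorded as using no rides.
4. Reconcile the fixed monthly wording of item 10 with the six-month pool in section 9.3.2.

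The cost is a sentence in each of two sections and a revision of one survey item. No new data collection is needed, because the plan already has the ride data going to the lead site.

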Appendix D: Data Safety Monitoring Plan

DFCI IRB Protocol #: 18-294

Appendix E. Ride Health Information Sheet80

INTRODUCTION

The Dana-Farber/Harvard Cancer Center Multi-Center Data and Safety Monitoring Plan (DF/HCC DSMP) outlines the procedures for conducting a DF/HCC Multi-Center research protocol. The DF/HCC DSMP serves as a reference for any sites external to DF/HCC that are participating in a DF/HCC clinical trial.

Purpose

To establish standards that will ensure that a Dana-Farber/Harvard Cancer Center Multi-Center protocol will comply with Federal Regulations, Health Insurance Portability and Accountability Act (HIPAA) requirements and applicable DF/HCC Standard Operating Procedures.

Multi-Center Data and Safety Monitoring Plan Definitions

DF/HCC Multi-Center Protocol: A research protocol in which one or more outside institutions are collaborating with Dana-Farber/Harvard Cancer Center where a DF/HCC investigator is the sponsor. DF/HCC includes Dana-Farber/Partners Cancer Care (DF/PCC) Network Clinical Trial Affiliates.

Lead Institution: One of the Dana-Farber/Harvard Cancer Center consortium members (Dana-Farber Cancer Institute (DFCI), Massachusetts General Hospital (MGH), Beth Israel Deaconess Medical Center (BIDMC), Boston Children's Hospital (BCH), Brigham and Women's Hospital (BWH) responsible for the coordination, development, submission, and approval of a protocol as well as its subsequent amendments per the DFCI IRB and applicable regulatory guidelines (CTEP, Food and Drug Administration (FDA), Office of Biotechnology Activities (OBA) etc.). The Lead Institution is typically the home of the DF/HCC Sponsor. The Lead Institution also typically serves as the Coordinating Center for the DF/HCC Multi-Center Protocol.

DF/HCC Sponsor: The person sponsoring the submitted Multi-Center protocol who takes responsibility for initiation, management and conduct of the protocol at all research locations. In applicable protocols, the DF/HCC Sponsor will serve as the single liaison with any regulatory agencies (i.e. CTEP Protocol and Information Office (PIO), FDA, OBA etc.). The DF/HCC Sponsor has ultimate authority over the protocol and is responsible for the conduct of the study at DF/HCC and all Participating Institutions. In most cases the DF/HCC Sponsor is the same person as the DF/HCC Overall Principal Investigator; however, both roles can be filled by two different people. For CTEP Protocols this person is called the Protocol Chair.

Participating Institution: An institution that is outside the DF/HCC and DF/PCC consortium that is collaborating with DF/HCC on a protocol where the sponsor is a DF/HCC Investigator. The Participating Institution acknowledges the DF/HCC Sponsor as having the ultimate authority and responsibility for the overall conduct of the study.

Coordinating Center: The entity (i.e. Lead Institution, Medical Monitor, Contract Research Organization (CRO), etc) that provides administrative support to the DF/HCC Sponsor in order

that he/she may fulfill the responsibilities outlined in the protocol document and DSMP, and as specified in applicable regulatory guidelines (i.e. CTEP Multi-Center Guidelines). In general, the Lead Institution is the Coordinating Center for the DF/HCC Multi-Center Protocol.

DF/HCC Office of Data Quality (ODQ): A group within DF/HCC responsible ensuring high-quality standards are used for data collection and the ongoing management of clinical trials, auditing, and data and safety monitoring. ODQ also coordinates quality assurance efforts related to multi-center clinical research.

DF/HCC Clinical Trials Research Informatics Office (CTRIO): A group within DF/HCC responsible for providing a comprehensive data management platform for managing clinical trial data.

GENERAL ROLES AND RESPONSIBILITIES

For DF/HCC Multi-Center Protocols, the DF/HCC Sponsor, the Coordinating Center, and the Participating Institutions are expected to adhere to the following general responsibilities:

DF/HCC Sponsor

The DF/HCC Sponsor, [name], will accept responsibility for all aspects of conducting a DF/HCC Multi-Center protocol which includes but is not limited to:

- Oversee the coordination, development, submission, and approval of the protocol as well as subsequent amendments.
- Ensure that the investigators, study team members, and Participating Institutions are qualified and appropriately resourced to conduct the protocol.
- Include the Multi-Center Data and Safety Monitoring Plan as an appendix to the protocol.
- Ensure all Participating Institutions are using the correct version of the protocol.
- Ensure that each participating investigator and study team member receives adequate protocol training (and/or a Site Initiation Visit prior to enrolling participants) and throughout trial's conduct as needed.
- Ensure the protocol will be provided to each participating site in a language understandable to all applicable site personnel when English is not the primary language.
- Monitor progress and overall conduct of the study at all Participating Institutions.
- Ensure all DFCI Institutional Review Board (IRB), DF/HCC and other applicable reporting requirements are met.
- Review data and maintain timely submission of data for study analysis.
- Ensure compliance with all requirements as set forth in the Code of Federal Regulations, applicable DF/HCC requirements, HIPAA requirements, and the approved protocol.

- Commit to the provision that the protocol will not be rewritten or modified by anyone other than the DF/HCC Sponsor.
- Identify and qualify Participating Institutions and obtain accrual commitments prior to extending the protocol to that site.
- Monitor accrual and address Participating Institutions that are not meeting their accrual requirements.

Coordinating Center

The general responsibilities of the Coordinating Center may include but are not limited to:

- Assist in protocol development.
- Review registration materials for eligibility and register participants from Participating Institutions in the DF/HCC clinical trial management system (CTMS).
- Distribute protocol and informed consent document updates to Participating Institutions as needed.
- Oversee the data collection process from Participating Institutions.
- Maintain documentation of deviations/violation submitted by Participating Institutions and provide to the DF/HCC Sponsor for timely review and submission to the DFCI IRB, as necessary.
- Provide Participating Institutions with information regarding DF/HCC requirements that they will be expected to comply with.
- Carry out plan to monitor Participating Institutions either by on-site or remote monitoring.
- Maintain Regulatory documents of all Participating Institutions which includes but is not limited to the following: local IRB approvals/notifications from all Participating Institutions, confirmation of Federalwide Assurances (FWAs) for all sites, Screening Logs for all sites, IRB approved consents for all sites
- Conduct regular communications with all Participating Institutions (conference calls, emails, etc) and maintain documentation all relevant communications.

Participating Institution

Each Participating Institution is expected to comply with all applicable federal regulations and DF/HCC requirements, the protocol and HIPAA requirements.

The general responsibilities for each Participating Institution may include but are not limited to:

- Document the delegation of research specific activities to study personnel.
- Commit to the accrual of participants to the protocol.
- Submit protocol and/or amendments to their local IRB of record.
- Maintain regulatory files as per sponsor requirements.
- Provide the Coordinating Center with regulatory documents or source documents as requested.

- Participate in protocol training prior to enrolling participants and throughout the trial as required (i.e. teleconferences).
- Update Coordinating Center with research staff changes on a timely basis.
- Submit protocol deviations and violations to local IRB per institutional requirements and to the DF/HCC Sponsor in accordance with DF/HCC requirements.
- Have office space, office equipment, and internet access that meet HIPAA standards.
- Participate in any quality assurance activities and meet with monitors or auditors at the conclusion of a visit to review findings.
- Promptly provide follow-up and/or corrective action plans for any monitoring queries or audit findings.

DF/HCC REQUIREMENTS FOR MULTI-CENTER PROTOCOLS

The following section will clarify DF/HCC Requirements and further detail the expectations for participating in a DF/HCC Multi-Center protocol.

Protocol Distribution

The Coordinating Center will distribute the final DFCI IRB approved protocol and any subsequent amended protocols to all Participating Institutions.

Protocol Revisions and Closures

The Participating Institutions will receive notification of protocol revisions and closures from the Coordinating Center. It is the individual Participating Institution's responsibility to notify its IRB of these revisions.

- **Non life-threatening revisions:** Participating Institutions will receive written notification of protocol revisions regarding non life-threatening events from the Coordinating Center. Non-life-threatening protocol revisions must be IRB approved and implemented within 90 days from receipt of the notification.
- **Revisions for life-threatening causes:** Participating Institutions will receive immediate notification from the Coordinating Center concerning protocol revisions required to protect lives with follow-up by fax, mail, e-mail, etc. Life-threatening protocol revisions will be implemented immediately followed by IRB request for approval.
- **Protocol closures and temporary holds:** Participating Institutions will receive notification of protocol closures and temporary holds from the Coordinating Center. Closures and holds will be effective immediately. In addition, the Coordinating Center, will update the Participating Institutions on an ongoing basis about protocol accrual data so that they will be aware of imminent protocol closures.

Informed Consent Requirements

The DF/HCC approved informed consent document will serve as a template for the informed consent for Participating Institutions. The Participating Institution consent form must follow the consent template as closely as possible and should adhere to specifications outlined in the DF/HCC Guidance Document on Model Consent Language for Investigator-Sponsored Multi-Center Trials. This document will be provided separately to each Participating Institution upon request.

Participating Institutions are to send their version of the informed consent document and HIPAA authorization, if a separate document, to the Coordinating Center for review and approval prior to submission to their local IRB. The approved consent form must also be submitted to the Coordinating Center after approval by the local IRB for all consent versions.

IRB Documentation

The DFCI IRB will act as the single IRB (sIRB) of record for this study (see protocol section 6).

The following must be on file with the Coordinating Center:

- Initial approval letter of the Participating Institution's IRB.
- Copy of the Informed Consent Form(s) approved by the Participating Institution's IRB.
- Participating Institution's IRB approval for all amendments.
- Annual approval letters by the Participating Institution's IRB.

IRB Re-Approval

Verification of IRB re-approval from the Participating Institutions is required in order to continue research activities. There is no grace period for continuing approvals.

The Coordinating Center will not register participants if a re-approval letter is not received from the Participating Institution on or before the anniversary of the previous approval date.

Participant Confidentiality and Authorization Statement

In 1996, congress passed the first federal law covering the privacy of health information known as the Health Insurance Portability and Accountability Act (HIPAA). Any information, related to the physical or mental health of an individual is called Protected Health Information (PHI). HIPAA outlines how and under what circumstances PHI can be used or disclosed.

In order for covered entities to use or disclose protected health information during the course of a study, the study participant must sign an authorization statement. This authorization statement may or may not be separate from the informed consent document. The Coordinating

Center, with the approval from the DFCI IRB, will provide a consent template, with information regarding authorization for the disclosure of protected health information.

The DF/HCC Sponsor will use all efforts to limit its use of protected health information in its trials. However, because of the nature of these trials, certain protected health information must be collected. DF/HCC has chosen to use authorizations, signed by the participant in the trial, rather than limited data sets with data use agreements.

DF/HCC Multi-Center Protocol Confidentiality

All documents, investigative reports, or information relating to the participant are strictly confidential. Whenever reasonably feasible, any participant specific reports submitted to the Coordinating Center should be de-identified. It is recommended that the assigned protocol case number (as described below) be used for all participant specific documents. Participant initials may be included or retained for cross verification of identification.

DF/HCC Multi-Center Protocol Registration Policy

Participant Registration and Randomization

Please see Section 5.3 of the protocol for instructions on the process to register and randomize patients.

Eligibility Exceptions

No exceptions to the eligibility requirements for a protocol without DFCI IRB approval will be permitted. All Participating Institutions are required to fully comply with this requirement. The process for requesting an eligibility exception is defined below.

DF/HCC Protocol Case Number/Study ID

At the time of registration, the following identifiers are required for all subjects: initials, date of birth, gender, race and ethnicity. Once eligibility has been established and the participant successfully registered, the participant is assigned a unique protocol case number/study ID. Participating Institutions should submit all de-identified subsequent communication and documents to the Coordinating Center, using this case number to identify the subject.

Protocol Deviations, Exceptions and Violations

Federal Regulations require an IRB to review proposed changes in a research activity to ensure that researchers do not initiate changes in approved research without IRB review and approval, except when necessary to eliminate apparent immediate hazards to the participant. DF/HCC requires all departures from the defined procedures set forth in the IRB approved protocol to be reported to the DF/HCC Sponsor, who in turn is responsible for reporting to the DFCI IRB.

For reporting purposes, DF/HCC uses the terms “violation”, “deviation” and “exception” to describe departures from a protocol. All Participating Institutions must adhere to these requirements for reporting to the DF/HCC Sponsor and will follow their institutional policy for reporting to their local IRB.

Definitions

Protocol Deviation: Any departure from the defined procedures set forth in the IRB-approved protocol which is *prospectively approved* prior to its implementation.

Protocol Exception: Any protocol deviation that relates to the eligibility criteria, e.g. enrollment of a participant who does not meet all inclusion/exclusion criteria.

Protocol Violation: Any protocol departure that was not *prospectively approved* by the IRB prior to its initiation or implementation.

Reporting Procedures

DF/HCC Sponsor: is responsible for ensuring that clear documentation is available in the medical record and/or regulatory documents to describe all protocol exceptions, deviations and violations. The DF/HCC Sponsor will also be responsible for ensuring that all protocol violations/deviations are promptly reported per DFCI IRB guidelines.

Participating Institutions: Protocol deviations require prospective approval from the DFCI IRB. The Participating Institution must submit the deviation request to the Coordinating Center who will then submit the deviation request to the DFCI IRB. Upon DFCI IRB approval the deviation is submitted to the Participating Institution IRB, per institutional policy. A copy of the Participating Institution’s IRB report and determination will be forwarded to the Coordinating Center within 10 business days after the original submission. The deviation may not be implemented without all required approvals.

All protocol violations must be sent to the Coordinating Center in a timely manner. The Coordinating Center will provide training for the requirements for the reporting of violations.

Coordinating Center: Upon receipt of the violation/deviation report from the Participating Institution, the Coordinating Center will submit the report to the DF/HCC Sponsor for review. Subsequently, the Participating Institution’s IRB violation/deviation report will be submitted to the DFCI IRB for review per DFCI IRB reporting guidelines.

Safety Assessments

The study teams at all participating institutions are responsible for protecting the safety, rights and well-being of study participants.

MONITORING: QUALITY CONTROL

The quality control process for a clinical trial requires verification of protocol compliance and data accuracy. The Coordinating Center, with the aid of the DF/HCC Office of Data Quality, provides quality control oversight for the protocol.

Ongoing Monitoring of Protocol Compliance

This is a small pilot multisite clinical trial of a supportive care intervention that provides minimal risk to participants and the prospect of direct benefit. As such, data monitoring will be carried out by a Data Safety Monitoring Committee (DSMC) composed of investigators representing different disciplines and expertise. The team will be comprised of Co-investigators: Drs. [name] and [name]; as well as three members who are not participating in the study ([name]; [name]; [name]) who will act as independent monitors. The committee will be convened at the beginning of the study via conference calls, to provide input and guidance on study conduct including quality assurance and safety issues as well as data management activities. All data reviewed by the DSMC will be blinded. DSMC virtual meetings will take place quarterly by videoconference calls.

The DSMC will be in charge of monitoring: 1) data quality for completeness, timeliness, and accuracy including conformance with informed consent requirements; 2) participants' accrual and retention; 3) adverse events; 4) participants' withdrawals, compliance issues or any complaints about the research; 5) intervention fidelity indicators; 6) compliance with data management procedures; 7) reviewing any protocol modifications/deviations that may occur between DSMC review periods.

Safety Monitoring: As above, we will utilize a DSMC to ensure that the trial is conducted according to the approved protocol. There are no physical risks to this study. There is a minimal risk of psychological distress to parents from completing in-depth interviews and surveys on the sensitive topic of basic resource needs and finances.

Data Management: Registration and patient tracking will be performed using DF/HCC ODQ OnCore system. This protocol will be registered with OnCore, allowing for centralized enrollment tracking in an ODQ-approved manner. The study team has been trained and has experience in using this system. All surveys and abstraction data will be stored in an institutionally-coordinated Research Electronic Data Capture (REDCap) database, which offers a secure web application. An institution-specific tracking log will also be kept as an Excel spreadsheet. These spreadsheets will be located on HIPAA-compliant DF/HCC servers. Physical study documents (i.e. paper surveys) will be stored in locked cabinets, and will only be identified by study ID.

Study data from all sites will be entered, stored, and managed in a password-protected REDCap database structured for this study on a secured server. REDCap is a research-focused electronic data capture system. Data will be verified both at point-of-entry and subsequently by a series of range checks, logical between-items checks, and outlier checks.

Quality Control Monitoring: The quality control process for a clinical trial requires verification of protocol compliance and data accuracy. The Coordinating Center (DFCI), with the aid of the ODQ provides quality control oversight for the protocol. Accrual will be monitored for each participating institution by the DSMC.

The Participating Institutions may be required to submit participant source documents to the Coordinating Center for monitoring. Participating Institution may also be subject to on-site monitoring conducted by the Coordinating Center.

Participating institutions will be required to participate in monthly Coordinating Center initiated teleconferences.

Remote Monitoring will be performed by central monitoring of REDCap survey completion (data are electronically entered and stored thus source verification is non-applicable unless paper/pencil survey administered due to technological challenges in which case these will be scanned and securely emailed to DFCI for central data entry and source documentation).

Monitoring Reports

The DF/HCC Sponsor will review all monitoring reports to ensure protocol compliance. The DF/HCC Sponsor may increase the monitoring activities at Participating Institutions that are unable to comply with the protocol, DF/HCC Sponsor requirements or federal and local regulations.

Accrual Monitoring

Prior to extending a protocol to an external site, the DF/HCC Sponsor will establish accrual requirements for each participating institution. Accrual will be monitored for each participating institution by the DF/HCC Sponsor or designee. Sites that are not meeting their accrual expectations may be subject to termination.

Accrual expectations for University Alabama Birmingham are as follows: Enrollment of 12 participants over 12 months.

AUDITING: QUALITY ASSURANCE

Auditing is a method of Quality Assurance and involves the systematic and independent examination of all trial related activities and documents. Audits determine if evaluated activities were appropriately conducted and whether data was generated, recorded and analyzed, and accurately reported per the protocol, applicable Policies, and the Code of Federal Regulations (CFR).

DF/HCC Internal Audits

All Participating Institutions are subject to audit by the DF/HCC Office of Data Quality (ODQ). Typically, approximately 3-4 participants would be audited at the site over a 2-day period. If violations which impact participant safety or the integrity of the study are found, more participant records may be audited.

Audit Notifications

It is the Participating Institution's responsibility to notify the Coordinating Center of all external audits or inspections (e.g., FDA, EMA, NCI) that involve this protocol. All institutions will forward a copy of final audit and/or re-audit reports and corrective action plans (if applicable) to the Coordinating Center, within 12 weeks after the audit date.

Audit Reports

